5.1.1. Dosage and Administration

All subjects will receive a single IV bolus administration of up to a target dose of 370 MBq (10 mCi) of ¹⁸F-AV-1451 Injection. Where necessary to minimize trial-wise radiation exposure or to comply with local regulations, lower dose may be planned with sponsor approval.

5.1.2. Rationale for Dosages

¹⁸F-AV-1451 will be administered IV up to a radioactive target dose of 370 MBq with a maximum human mass dose (MHD) limited to 20 µg of compound by weight. This dose is 150 fold lower than the NOAEL observed in the rat single dose toxicity study and is 50 fold lower than the NOAEL observed in the rat and dog repeat dose toxicity studies.

Human dosimetry has been obtained in nine subjects. The results estimated an Effective Dose of 8.92 mSv for an anticipated 370 MBq (10 mCi) injection and is comparable to the effective dose of approved ¹⁸F-labeled compounds such as FDG and florbetapir F 18 injection.

The proposed dose has been shown to be well tolerated and to have acceptable image quality in preliminary human studies.

5.2. Selection of Subjects

Subjects should meet inclusion and exclusion criteria for the companion protocol, and in addition:

5.2.1. Inclusion Criteria

Subjects who meet all of the following criteria are eligible to enroll in this study:

1. Male or female subjects at least 18 years of age;
2. Subjects who sign an IRB approved informed consent prior to any study procedures. Where subjects are deemed incapable of informed consent, a legally authorized representative may provide consent, with the subject's documented assent;
3. Subjects who have historical volumetric brain MRI images obtained as part of the site's companion protocol available for submission to Avid; and
4. Subjects who in the opinion of the investigator can tolerate the PET scan procedures.

5.2.2. Exclusion Criteria

Subjects will be excluded from enrollment if they:

1. Have clinically significant cardiac, hepatic, renal, pulmonary, metabolic, or endocrine disturbances as indicated by history, which in the opinion of the investigator might pose a potential safety risk to the subject;
2. Have either: 1) Screening ECG with QTc > 450 msec if male or QTc > 470 msec if female; or 2) A history of additional risk factors for Torsades de Pointes (TdP) (e.g., hypokalemia, family history of Long QT syndrome) or are taking drugs that

- are known to cause QT-prolongation (a list of prohibited and discouraged medications is provided by the Sponsor); Patients with a prolonged QTc interval in the setting of intraventricular conduction block (examples RBBB or LBBB), may be enrolled with sponsor approval;
3. Have a history of drug or alcohol dependence within the last year, or prior prolonged history of dependence unless approved by the sponsor;
 4. Are females of childbearing potential who are not surgically sterile, not refraining from sexual activity or not using reliable methods of contraception. Females of childbearing potential must not be pregnant (negative serum or urine β -HCG at the time of screening and negative serum or urine β -HCG on imaging day) or breastfeeding at screening. Females must agree to avoid becoming pregnant, and both females and males must agree to refrain from sexual activity or to use reliable contraceptive methods for 90 days following administration of ^{18}F -AV-1451 Injection;
 5. Have a history of relevant severe drug allergy or hypersensitivity (Relevant severe drug allergies should be determined by the PI, and any questions about a subject's eligibility can be directed to Avid. If a subject has a history of severe drug allergies, it may be dangerous for them to participate in a study);
 6. Are patients who have received an investigational medication under an FDA IND protocol within 30 days prior to the planned imaging session for this study, with the exception of medications allowed in the companion study and approval from sponsor. Additionally, the time between the last dose of the previous experimental medication and imaging must be at least equal to 5 times the terminal half-life of the previous experimental medication.
 7. Are patients with current clinically significant unstable medical comorbidities, as indicated by history or physical exam that pose a potential safety risk to the subject.
 8. Are patients who have received a radiopharmaceutical for imaging or therapy within the past 24 hours prior to the imaging session for this study. If another radiotracer is required in the companion protocol, patients may be able to receive a radiopharmaceutical for imaging or therapy within the 24 hours prior to the imaging session with prior sponsor approval;
 9. Are patients who, in the opinion of the investigator, are otherwise unsuitable for a study of this type.

5.3. Prior and Concomitant Therapy

Except as noted below, all medications (prescription or OTC) that have been started prior to screening may be continued during the course of the trial. Attempts should be made to keep the dosage and administration stable throughout the trial (from screening through the end of the imaging session). Stable is generally defined as 2 weeks on therapy. All medications that are continued from the start of the trial, or that are started during the trial

(other than the study medication), must be documented on the Concomitant Medication Page of the Electronic Case Report Form (eCRF).

- Patients with AD may be on a stable dose of an anticholinesterase and/or Namenda, and may be taking vitamin E at the time of imaging.
- Investigators should carefully consider whether subjects requiring psychotropic medications for behavioral control will be able to complete the imaging session and necessary procedures such as cognitive testing.
- Subjects who are taking drugs that are known to cause QT-prolongation may not be enrolled in the study (a list of prohibited and discouraged medications is provided by the Sponsor).

5.4. Removal of Subjects from Trial

Subjects must be removed from the trial if:

1. Informed consent is withdrawn; or
2. The investigator, or the sponsor, believes it is in the best interest of the subject to be removed from the trial.
3. Subjects who are being considered for a follow up AV-1451 scan within this protocol must meet all inclusion/exclusion criteria at the time of the second imaging session.

Subjects may be withdrawn from the trial if a SAE occurs. The date and reason for discontinuation should be noted on the eCRF. Subjects who discontinue prematurely should be seen for a final evaluation.

5.5. Premature Termination of Trial/Closure of Center

The sponsor may discontinue the trial at any time. Reasons for discontinuation of the trial may include, but are not limited to, new information on safety or efficacy, requests from regulatory authorities, or changes in business priorities. Additional reasons for center closure may include, but are not limited to, excessive protocol violations, inadequate regard for subject safety, failure to follow recommended procedures (e.g., documentation), failure or inability to accommodate Avid/Contract Research Organization (CRO) monitors or to provide required access to data and source documents, staff turnover or inadequate staffing, and inadequate enrollment. Except in cases affecting subject safety, the investigator may complete final study evaluations for ongoing subjects. In all cases of center or study termination, appropriate steps will be taken to ensure the safety of study subjects.

6. WARNINGS/PRECAUTIONS

The most up-to-date and complete information regarding the use of ¹⁸F-AV-1451 Injection can be found in the investigator's brochure.

In brief, ^{18}F -AV-1451 Injection is an experimental imaging agent that will be used at relatively low (tracer) doses. However, because ^{18}F -AV-1451 Injection is in the early stages of clinical investigation, it is recommended that subjects receiving ^{18}F -AV-1451 Injection be followed closely by means of adverse event reporting and vital signs.

There are no data on the effects of ^{18}F -AV-1451 Injection in human perinatal development. For this reason, females must avoid becoming pregnant. Both females and males must use adequate contraceptive methods for 90 days after administration of ^{18}F -AV-1451 Injection. ^{18}F -AV-1451 Injection must not be administered to females who are pregnant, or lactating.

7. PROCEDURES AND METHODS

7.1. Assessment Periods (See Section 11.2, Trial Flow Chart)

The study will consist of the following sequence of activities:

7.1.1. Screening:

Screening may take place over several days. All screening assessments will preferably be performed within 30 days prior to the PET imaging session. Some screening assessments may be performed on the imaging day prior to injection with sponsor approval.

Screening assessments will include:

- Informed consent;
- Demographics (age, gender, education, race, ethnicity);
- Medical history, concomitant medications;
- Disease history (date/months since symptom onset, date/months since diagnosis, family history of relevant neurologic disease);
- An ECG will be performed to assess the subject's cardiac status. If an ECG was performed within the last 6 months and is available for review, the ECG does not need to be repeated;
- Cognitive status interview, including MMSE and OSU TBI-ID;
- Where appropriate, informant interview with family member or close friend who is familiar with subject's everyday functioning abilities;
- Urine or serum pregnancy test (women of childbearing potential);
- A physician will see the patient during the screening visit.

Demographic information, cognitive status assessment, MMSE, and OSU TBI-ID collected within the last 60 days as part of a companion protocol or clinic visit need not be repeated.

7.1.2. Imaging Visit

¹⁸F-AV-1451 PET Imaging Visit

The following assessments will be performed for all subjects:

- Females of childbearing potential will have a urine or serum pregnancy test prior to injection (the result must be negative for the subject to be administered ¹⁸F-AV-1451);
- Vital signs will be taken in a supine position immediately prior to administration of ¹⁸F-AV-1451 (within 30 minutes prior to injection) and at the completion of imaging at discharge.
- Body weight and height will be measured prior to injection.
- ¹⁸F-AV-1451 will be administered, a 20 minute dynamic image will begin approximately 80 minutes post-injection. The images will be reconstructed immediately after the scan. With sponsor approval, sites may elect an alternative imaging protocol with additional time points. All datasets will be submitted to the sponsor for analysis.
- Subjects will be observed continuously for signs of adverse events, or serious adverse events;
- A physician will see the patient prior to dosing and prior to discharge.

7.1.3. Follow-Up:

A follow-up phone call to the subject, or designated decision maker, will be conducted between 2 or 3 business days after imaging day, but not before 48 hours post-injection, to confirm subject well-being and to collect information about any new adverse events. If both of these days are not business days, the follow-up phone call can occur the following business day.

7.1.4. Repeat Imaging:

Longitudinal imaging studies may be conducted under protocol ¹⁸F-AV-1451-A14, with prior sponsor approval. In these studies subjects may have up to two imaging sessions within a 12 month timeframe. If the second scan is obtained more than 3 months after the previous scan then the MMSE should be repeated and updates to the medical history, OSU-TBI and concomitant medications will be collected. Procedures for each imaging day will be identical to those described above.

7.2. Observations and Measurements

Informed Consent

Potential subjects will be allowed to read a written informed consent form. The principal investigator, or designee, will explain all study procedures, risks, and alternative therapies to subject. The subject will have an opportunity to have all questions answered. The appropriate parties will then sign and date the informed consent form, indicating

their willingness to participate in the study (see Section 7.5). A copy of the signed informed consent will be given to the subject.

All informed consent forms must be approved by Avid, or designee, and by the appropriate Institutional Review Board (IRB) prior to use.

Medical History

The investigator, or designee, will obtain an updated history at the screening visit.

- Relevant demographic information
- Review of body systems
- Social history
- Medical and surgical history, including medical care for head trauma
- Concurrent medications

Whenever possible, the medical history will be confirmed by medical records.

Electrocardiogram

A resting ECG will be recorded at screening if a previous ECG performed within the last 6 months is not available for review.

MRI

Electronic copies of historical volumetric brain MRI scans obtained as part of the site's companion protocol will be submitted to Avid, or designated imaging core lab.

Vital Signs

Vital signs (pulse rate, respiratory rate, blood pressure) will be taken as part of the imaging day procedures in the supine position prior to injection and at the completion of imaging at discharge.

Height and Weight

At the imaging visit (prior to ¹⁸F-AV-1451 dose administration) body weight and height will be measured, lightly clothed.

Mini-Mental State Examination (MMSE)

The MMSE (Folstein et al., 1975) is a brief instrument used to assess cognitive function in elderly patients. The instrument is divided into 2 sections. The first section measures orientation, memory, and attention. The maximum score for the first section is 21. The second section tests the ability of the patient to name objects, follow verbal and written

commands, write a sentence, and copy figures. The maximum score for the second section is 9. The range for the total MMSE score is 0 to 30.

Ohio State University Traumatic Brain Injury Identification Method (OSU TBI-ID)

The OSU TBI-ID (Corrigan and Bogner, 2007) short version will be used to screen for a history of traumatic brain injury. It is the briefest version that still provides several summary indices on which the original version was validated. To shorten the instrument, TBIs resulting in loss of consciousness are emphasized over less severe injuries.

Physician Visit

A physician must see the subject at screening, prior to drug administration and at study end, prior to discharge from the ^{18}F -AV-1451 imaging session. At discharge, the physician should review all safety data and briefly examine/query the subject regarding potential adverse events, or other treatment issues.

Pregnancy Testing

Serum beta hCG or Urine beta hCG: performed at screening and imaging day prior to injection for females of childbearing potential (defined as pre-menopausal or less than 2 years post-menopausal or not surgically sterile).

7.3. Protocol for Image Collection

The sponsor will prepare and distribute imaging manuals for ^{18}F -AV-1451 image acquisition parameters and transmission procedures prior to site initiation.

7.4. Good Clinical Practice and Monitoring

All clinical studies performed under the direction of Avid/CRO will be conducted in accordance with applicable regulatory requirements and International Conference on Harmonization (ICH) Good Clinical Practice (GCP) and Avid/CRO Standard Operating Procedures (SOP).

This includes:

1. IRB approval: An investigation will be initiated at a study site only after the IRB for that study site has given their written approval of the protocol and informed consent;
2. Informed Consent: Study procedures will not be initiated until the subject signs the informed consent form;
3. Recording and monitoring of adverse events as outlined in Section 7.7.3 including the notification of study site clinical investigators, local IRBs and the FDA regarding serious adverse event;
4. Avid RP's obligation to monitor the participating center on a regular basis; and

5. The termination of a center, or the trial, if conditions apply, as outlined in Section 5.6.

7.5. Informed Consent and Subject Information

Potential subjects, or their legally authorized representative (as appropriate), will be allowed to read a written informed consent form. The principal investigator, or designee, will explain all study procedures, risks, and alternative therapies. The subject, and legally authorized representative, will have an opportunity to have all questions answered by a physician. The subject will then sign and date the informed consent form, indicating willingness to participate in the study.

All informed consent forms must be approved by Avid, or designee, and by the appropriate Institutional Review Board (IRB). No study related procedures shall be performed prior to completion of the informed consent process, and signing of the consent form. A copy of the signed informed consent should be given to the patient for their records.

7.6. Documentation

¹⁸F-AV-1451 scans will be saved in an appropriate electronic format as specified in the imaging manuals. All other data required by the protocol will be recorded in the eCRFs. All data in the eCRFs will be substantiated by “source documents,” which consist of the subject’s medical files, laboratory result sheets, ECG tracings, etc. All source documentation must be available to Avid, and designees. Completed source documents and eCRFs may need to be made available and complete for an audit by the FDA, other international regulatory authorities, or Avid at any time. eCRFs and all other records must be filed in accordance with applicable laws and regulations (see Section 10.6)

7.7. Adverse Events (AE)

Avid’s standards for recording and reporting adverse events (AEs) are to be followed regardless of applicable regulatory requirements that may be less stringent. All AEs must be fully recorded on the adverse event eCRFs. Investigators will be instructed to report to Avid or its designee their assessment of the potential relatedness of each AE to study drug or protocol procedure via electronic data entry. If a patient’s treatment is discontinued as a result of an AE, study site personnel must clearly report to Avid or its designee via electronic data entry the circumstances and data leading to any such discontinuation of treatment. In cases where the investigator notices an unanticipated benefit to the patient, study site personnel should report “unexpected benefit” with the actual event term to Avid or its designee (for example, the complete actual term would be “unexpected benefit- sleeping longer”).

Laboratory test abnormalities considered by the Investigator to be clinically relevant should be reported on the adverse event eCRFs. Signs and symptoms of each AE should be described in detail (e.g., start and stop dates/time, severity/intensity, relationship to study drug, action taken, and outcome). Additionally, any clinically significant findings from laboratory evaluations, vital sign measurements, or other study procedures including those that result in a diagnosis should be reported as an AE to Avid, or its designee.

7.7.1. Adverse Event Monitoring

Each patient must be carefully monitored for adverse events. This includes clinical laboratory test variables. An assessment must be made of the severity/intensity and relationship to the administration of the study drug.

7.7.2. Adverse Event Definitions

Adverse Events

An adverse event is any undesirable experience occurring to a subject during a clinical trial, whether or not considered related to the study drug.

For reporting purposes, Avid will distinguish among pre-existing conditions, trial-emergent adverse events and treatment-emergent adverse events.

Pre-existing conditions (i.e., undesirable experiences, signs or symptoms that begin prior to the Screening Visit) will be recorded on the medical history eCRF pages. During the study, site personnel will record any change in the condition(s) and occurrence and nature of any AEs. Signs and symptoms that are believed to be due to the pre-existing condition under study (started prior to dose of study medication) do not have to be recorded in the AEs section of the eCRF, unless there is an increasing in frequency and severity.

Trial-emergent adverse events are undesirable experiences, signs or symptoms that begin, or worsen in intensity or frequency, after the informed consent, and prior to administration of study drug (^{18}F -AV-1451) at the imaging visit. These will be recorded on the adverse event eCRFs.

Treatment-emergent adverse events are undesirable experiences, signs, or symptoms associated with the use of a study drugs. For the purposes of this study an adverse event will be considered associated with the use of ^{18}F -AV-1451 if it begins or worsens in intensity or frequency within 48 hours after the administration of ^{18}F -AV-1451. Adverse experiences that occur after administration of study drug but outside the 48 hour reporting window will not be reported unless the investigator believes they are attributable to the drug.

The end of study for the purpose of adverse event reporting is defined as 48 hours after the administration of ^{18}F -AV-1451 Injection.

Serious Adverse Event (SAE)

A SAE is an AE that results in one of the following outcomes or constitutes one of the following events:

- Death;
- Initial or prolonged inpatient hospitalization (other than that required by protocol; “social hospitalization” or any hospitalization for non-medical reasons does not constitute a SAE);
- A life-threatening experience (that is, immediate risk of dying);
- Persistent or significant disability/incapacity;

- Congenital anomaly/birth defect;
- Considered significant by the investigator for any other reason.

Important medical events that may not result in death, be life-threatening, or require hospitalization may be considered serious adverse drug events when, based upon appropriate medical judgment, they may jeopardize the patient and may require medical, or surgical, intervention to prevent one of the outcomes listed in this definition.

Unexpected Adverse Event

An unexpected adverse event is an adverse event not previously reported or an adverse event that occurs with specificity, severity, or frequency that is not consistent with the current investigator's brochure.

Relationship to Study Drug

Investigators will be instructed to report their assessment of the potential relatedness of each adverse event to protocol procedure or study drug. The assessment of the relationship of an adverse event to the administration of the study drug is a clinical decision based on all available information at the time of the completion of the eCRF.

Intensity/Severity of an Adverse Event

In addition to assessing the relationship of the administration of the study drug to adverse events, an assessment is required of the intensity (severity) of the event.

The following classifications should be used:

Mild:

A mild adverse event is an adverse event, usually transient in nature and generally not interfering with normal activities.

Moderate:

A moderate adverse event is an adverse event that is sufficiently discomforting to interfere with normal activities.

Severe:

A severe adverse event is an adverse event that incapacitates the subject and prevents normal activities. Note that a severe event is not necessarily a serious event. Nor must a serious event necessarily be severe.

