7.7.3. Adverse Event Documentation

All adverse events must be fully recorded on the adverse event eCRFs. Documentation must be supported by an entry in the subject file. Laboratory tests, vital signs and ECG abnormalities considered by the Investigator to be clinically relevant should be reported on the adverse event eCRFs. Signs and symptoms of each AE should be described in detail (e.g., start and stop dates, severity/intensity, relationship to study drug, action taken, and outcome).

Adverse events and laboratory test abnormalities fulfilling the definition of a serious adverse event should, in addition, be reported on the Serious Adverse Event Reporting Form.

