10.7. Adverse Events

All adverse events encountered during the clinical trial must be documented on the eCRF, whether or not considered drug-related.

Eli Lilly must be notified immediately (as soon as possible, and in all cases within 24 hours) of a drug experience, condition, development, or event, which is considered serious. Eli Lilly must be notified immediately of any findings with the use of the drug that may suggest significant hazards, contraindications, adverse drug reactions (ADRs) and precautions pertinent to the safety of the drug. The investigator will be requested to

complete a separate report form in addition to the information on the eCRF. See section 7.7.4 for reporting serious adverse events.

If a SAE is determined to be unexpected (not previously reported or described by Avid), and study drug-related, Eli Lilly will notify the investigator in writing. The investigator should forward this notification to the IRB within 24 hours of receipt.

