6.6 Safety Assessments

6.6.1 *Extent of Exposure and Compliance to Study Treatment*

During the flortaucipir imaging sessions, all subjects received a single IV bolus administration target dose of 240 (6.49 mCi) or 370 MBq (10 mCi) of flortaucipir injection.

6.6.2 *Adverse Events*

An AE is any undesirable experience occurring to a subject during a clinical trial, whether considered related to the study drug or not. AEs are classed by severity and seriousness.

Treatment-emergent adverse events (TEAE) are any untoward medical occurrences associated with the use of a drug in humans. For the purposes of this study, untoward medical occurrences will be considered associated with the use of flortaucipir, and thus be reported as TEAEs, if they occur within 48 hours after administration of the PET tracer. The end of study for the purpose of AE reporting is defined as 48 hours after the administration of flortaucipir injection.

The investigator's verbatim term of both serious and non-AEs will be mapped to system organ class (SOC) and preferred terms (PT) using the Medical Dictionary for Regulatory Activities (MedDRA) Version 17.1.

Investigators will be instructed to report their assessment of the potential relatedness of each AE to protocol procedure and flortaucipir. The assessment of the relationship of an AE to the administration of the flortaucipir is a clinical decision based on all available information at the time of the completion of the eCRF.

Investigators will also assess the severity of AE. Severity is classified as mild/moderate/severe (increasing severity).

Serious AEs (SAEs) are events that result in one of the following outcomes or constitute one of the following events:

- Death
- Initial or prolonged hospitalization (other than that required by protocol; "social hospitalization" or any hospitalization for non-medical reasons does not constitute an SAE)
- A life-threatening experience (that is, immediate risk of dying)
- Persistent or significant disability/incapacity
- Congenital anomaly/birth defect
- Considered significant by the investigator for any other reason

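### Protocol 7.7.2 lets symptoms of the condition under study stay off the AE page unless frequency and severity both rise, yet a rise in either one makes a treatment-emergent event

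*Protocol*

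**What the plan says.** Four sets of statements bear on this point.

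- **The exemption.** Under Protocol 7.7.2, signs and symptoms believed to come from the pre-existing condition under study, with onset before dosing, "do not have to be recorded in the AEs section of the eCRF, unless there is an increasing in frequency and severity". The sentence before it says that during the study "site personnel will record any change in the condition(s) and occurrence and nature of any AEs", but names no eCRF page for the change in condition.
- **The definitions in the same section.** Trial-emergent events are those that begin, or "worsen in intensity or frequency, after the informed consent, and prior to administration of study drug", and they go on the AE eCRF. An event counts as treatment-emergent "if it begins or worsens in intensity or frequency within 48 hours after the administration".
- **The general recording rules.** Protocol 7.7.3 states: "All adverse events must be fully recorded on the adverse event eCRFs". Section 7.7 has the same rule. Section 10.7 adds: "All adverse events encountered during the clinical trial must be documented on the eCRF, whether or not considered drug-related". None of the three mentions the exemption.
- **The SAP.** Section 6.6.2 treats untoward occurrences as TEAEs "if they occur within 48 hours after administration of the PET tracer" and does not mention worsening. Section 8.5.2 builds the TEAE tables and the AE listing from AEs. Medical history (8.3.2) and follow-up contact data (8.5.4) are only listed.

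**The concern.** The definitions join frequency and intensity with *or*; the exemption joins them with *and*. An event can satisfy the first and still be excused from recording by the second. For example, a subject in a traumatic brain injury companion study who usually has a mild daily headache has one severe headache a few hours after injection. If the investigator believes it is due to the old injury, intensity has risen and frequency has not. By the definition it is treatment-emergent; by the exemption it need not be entered.

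Expanding the safety database is one of the two primary objectives, and standardized data collection is part of the other. A rule that lets qualifying events go unentered bears on the first, and a rule that sites can apply in two ways bears on the second. An event that was never entered also carries no relatedness or severity assessment on the AE page, and no later change to the analysis can supply one.

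**Working it through.** No arithmetic applies, because the documents state no event rate or count for such events. The check sets the two rules side by side for a non-serious symptom that is attributed to the condition under study and changes within 48 hours of dosing.

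| Change in the symptom | Treatment-emergent under Protocol 7.7.2 (either one) | AE-section entry required by the exemption (both) |
|---|---|---|
| Frequency only | Yes | No |
| Severity only | Yes | No |
| Both | Yes | Yes |
| Neither | No | No |

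Three patterns meet the definition, and two of those three fall under the exemption. This counts patterns, not events.

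Next, does anything else in the documents close the gap?

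1. *Recording any change in the condition (7.7.2).* No page is named. The flow chart in Protocol 11.2 schedules medical history at screening only, and section 7.1.4 plans an update only when a second scan follows more than 3 months after the previous one. A change noted outside the AE page has no defined route into the TEAE tables.
2. *The all-AE rules (7.7, 7.7.3, 10.7).* They conflict with the exemption rather than resolve it, since no order of precedence is given.
3. *The follow-up call (7.1.3).* It asks about new adverse events. That does not clearly prompt for worsening of an old symptom.
4. *Serious events (7.7.4).* SAEs are collected for 48 hours after dosing whatever the investigator thinks of causation. This closes the gap for serious worsening.
5. *SAP 6.6.2.* It has no worsening limb, and the rules in SAP 8.5.2.7 work from the AE start date. A worsening that is recorded but carries the symptom's old onset date would appear in the AE listing and could still be missed in the TEAE tables. Correcting the protocol alone is therefore not enough.

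What remains open is non-serious worsening, on one dimension only, attributed to the condition under study.

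**The case against.** The strongest reply is that the exemption permits omission and does not order it. Sections 7.7, 7.7.3 and 10.7 tell sites to record everything, a physician questions the subject before discharge (7.2), and AE assessment is scheduled at every time point (11.2). On that view this is loose drafting with little effect. Much of this stands. A reader might infer that such events never reach the AE page, or that the TEAE rate is shown to be biased low. The documents support neither: a site that follows the general rules will enter the event. They do support that a site which omits it has also followed the protocol.

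The exemption is also narrow. It covers only symptoms believed due to the condition under study, so a headache that the investigator does not attribute to that condition must be recorded. This stands and limits the point. One consequence remains: the treatment-emergent definition rests on timing alone, and the exemption lets a judgement about cause override it.

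A reader might also infer that the double condition is rarely met within 48 hours. That is not shown, since a daily symptom can visibly become more frequent in that time.

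Finally, a reader might infer that the loss falls only on impaired subjects, because cognitively normal subjects have no condition under study. Appendix 11.3 defines the normal group by MMSE, history and testing, not by the absence of brain injury or depression, and the term *condition under study* is not defined. SAP 8.5.2 specifies no comparison of TEAEs between groups. Protocol 8.1 does ask for summaries by diagnostic group, so uneven capture would matter if it occurred.

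**Conclusion.** The inconsistency is real and lies within a single section of the protocol; nothing else in either document reconciles it. Non-serious worsening in frequency or in severity alone, attributed to the condition under study, can be treatment-emergent and yet need not be entered or tabulated. Sites may differ in what they record.

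The size of the loss cannot be estimated. With about 179 dosed subjects (SAP 4.4), each subject whose only TEAE went unrecorded would lower the subject-level rate by 1/179 = 0.56 percentage points. That gives the scale of one event and says nothing about how many there were. Given a single tracer dose, a 48-hour window and the limits above, the effect is probably small. A difference between diagnosis groups is possible but not established.

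The conclusion assumes that *and* in the exemption is read literally and that any site instructions outside these documents do not already say otherwise. The correction is still worth making, because it costs almost nothing and concerns a primary objective.

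**What to change.** 1. In Protocol 7.7.2, change the end of the exemption to: *unless there is an increase in frequency or severity (intensity)*. This brings it into line with the trial-emergent and treatment-emergent definitions beside it. Make 7.7, 7.7.3 and 10.7 consistent with it, and carry the wording into any site instructions for the eCRF.
2. In SAP 6.6.2, extend the TEAE definition to events that begin or worsen in intensity or frequency in the 48-hour window. State that a worsening is dated from when it started, so that the rules in 8.5.2.7 do not classify it by the old onset date.
3. The SAP describes dosing in the past tense, so a protocol edit may change no data. For data already collected, query source, medical-history and follow-up-call entries for worsening within 48 hours of injection, and enter qualifying events as AEs. If that is not feasible, report the recording rule as a limitation of the TEAE rates.

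The cost is one word in the protocol, one clause in the SAP with its dating rule, and a targeted query. The downside is a slightly higher TEAE count, some of it natural fluctuation of existing symptoms.
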